7.1. DNDi study treatment

Name: Miltefosine (Impavido®)

Class: Phosphocholine analogue.

Mechanism of action: interferes with the synthesis and metabolism of phospholipids.

It may also interfere with the parasite's membrane signal transduction, and

glycosylphosphatidylinositol anchor biosynthesis.

Commercial source: Paladin labs and Knight Therapeutics Inc.

Product appearance: comes as 10mg and 50mg capsules in pack of 56 capsules sealed in 8 aluminum blister stripes, each containing 7 capsules.

Administration: oral treatment

For MF, there are no known interactions with other commonly used medications, though this cannot be excluded.

Confidential Page 32 of 68

Name: **Paromomycin** Class: Aminoglycoside

Mechanism of action: inhibits protein synthesis by binding to 16S ribosomal RNA.

Commercial source: Gland Pharma, India; distributed by IDA Foundation.

Product appearance: Each box of paromomycin contains a pack of 10 amber-colored glass ampoules containing 750 mg of paromomycin base in 2 ml (375 mg/ml) equivalent to 1 g of paromomycin sulphate in 2 ml (500 mg/ml).

The 20 mg/kg sulfate is equivalent to 15 mg/kg of base.

Administration: intramuscular injection.

Name: Sodium Stibogluconate

Class: Pentavalent antimonial

Mechanism of action: decrease in ATP and GTP synthesis contributes to decreased macromolecular synthesis and to decreased *Leishmania* viability.

Commercial source: Albert David Ltd., India; distributed by IDA Foundation.

Product appearance: A faintly straw coloured fluid in a multi-dose brown opaque vial of 30ml containing SSG BP equivalent to 100mg pentavalent antimony in each ml (total 3g).

Administration: Given IV (slow over 5 minutes) or IM at a daily dose of 20mg/kg body weight.

7.2. Doses and treatment regimens

7.2.1 Test arms

Arm 1: Paromomycin 20 mg/kg/d IM q.d. for 14 days combined with oral miltefosine allometric dosing b.i.d. for 14 days

Arm 2: Paromomycin 20 mg/kg/d IM q.d. for 14 days combined with oral miltefosine allometric dosing b.i.d. for 28 days (recruitment is now discontinued in this arm)

MF dosing will be defined as follows:

- Patients <30 kg: the allometric MF daily dose will be calculated according to subject's weight, height and sex
- Patients ≥ 30 to <45 kg: 100 mg/day
- Patients ≥ 45 kg: 150 mg/day

PM and MF will be administered together, both starting at D1. PM dosage will be 20 mg/kg/d for 14 days administered intramuscularly, whereas MF allometric dose will be administered orally for 14 days in arm 1 (it used to be administered for 28 days in arm 2).

Patients are hospitalized for 14 days of PM and MF treatment in both arm 1 and arm 2. The MF treatment will start at the same time as the PM treatment and for arm 2 it used to continue on an out-patient basis until completion of the 28 days treatment.

Miltefosine administration

MF will be administered orally for 14 days in arm 1 and used to be administered for 28 days in arm 2.

Confidential Page 33 of 68

For patients less than 30 kg, the allometric dose will be defined according to weight, height and sex as indicated in Table 1, divided in 2 administrations per day for 14 days in arm 1 or 28 days in arm 2 (not applicable now recruitment has been discontinued in arm 2).

Table 1 - Daily allometric miltefosine dose for female children based on fat-free mass

FEMALE									
HT (cm)	80-89	90-99	100-109	110-119	120-129	130-139	140-149	150-159	160
WT (kg)									
7									
8	30								
9	30			RISK (OF SF\	/FRF N	ΛΑΙ ΝΙ	JTRITI	ON
10		40		111011		THE WHO F			
10	30	40	40		KEFEK IU	THE WHO F	KEFEKENCE	CURVES	
	40		40 40						
12 13	40 40	40 40	40						
14	40	40	40	50					
15	40	40	50	50					
16	40	50	50	50					
17	40	50	50	50	50				
18	50	50	50	50	60				
19	50	50	50	60	60				
20	50	50	50	60	60				
21	50	50	60	60	60	60			
22	50	50	60	60	60				
23	50	50	60	60	60		70		
24	50	50	60	60	60	70	70		
25	50	60	60	60	70		70		
26	50	60	60	60	70		70	70	
27	50	60	60	70	70		70	80	
28	50	60	60	70	70	70	80	80	
29	50	60	60	70	70		80	80	
30	50	60	60	70	70	80	80	80	80

Confidential Page 34 of 68

Table 2 - Daily allometric miltefosine dose for male children based on fat-free mass

MALE									
HT (cm)	80-89	90-99	100-109	110-119	120-129	130-139	140-149	150-159	160
WT (kg)									
7									
8	40								
9	40			RISK (OF SE\	/ERE N	/ALNU	JTRITI	ON
10	40	40			REFER TO	THE WHO F	REFERENCE	CURVES	
11	40	40							
12	40	50							
13	50	50	50						
14	50	50	50						
15	50	50	60	60					
16	50	50	60	60					
17	50	60	60	60					
18	50	60	60	60	70				
19	50	60	60	70	70				
20	50	60	60	70	70				
21	60	60	60	70	70	70			
22	60	60	70	70	70	80			
23	60	60	70	70	80	80			
24	60	60	70	70	80	80	80		
25	60	60	70	70		80	80		
26	60	70	70	80	80	80	100		
27	60	70	70	80	80	80	100		
28	60	70	70	80	80	100	100	100	
29	60	70	70	80	80	100	100	100	
30	60	70	80	80	100	100	100	100	

MF 10 mg and 50 mg strengths will be supplied through MSF Supply, Belgium, and Knight Therapeutics, US respectively in alu/alu blister packs of 56 capsules.

Administration of the daily dosage must be divided in 2 administrations, during or after a meal, to avoid direct gastrointestinal adverse effects of MF, as follows:

Total daily dose, divided:	30mg	40mg	50mg	60mg	70mg	80mg	100mg	150mg
Morning (breakfast)	2x 10mg	2x 10mg	1x 50mg	1x 50mg	1x 50mg	1x 50mg	1x 50mg	2x 50mg
Afternoon (dinner)	1x 10mg	2x 10mg		1x 10mg	2x 10mg	3x 10mg	1x 50mg	1x 50mg

Confidential Page 35 of 68

During the 14 days of hospitalization, administrations for all patient's arms will be directly observed by the study nurse to assure compliance. The number of capsules administered (morning and afternoon), the time of administration and any vomiting episode will be documented in a patient dispensing log. After each drug intake the patients will be observed for vomiting for 30 minutes. All vomiting episodes will be recorded. In case of vomiting within 30 minutes after intake, the dose will be readministered. If a repeated vomiting occurs (vomiting after re-dose) the treatment will not be re-administered.

Compliance will be assessed by total dose taken by the patient. Full compliance will be considered if 90-110% of the prescribed dose is administered.

If the patient vomits a dose within 30min of drug intake and is re-dosed (without vomiting this 2nd re-dose), the re-dose will be considered for compliance. However, if the patient is not re-dosed within 30min or if s/he vomits the re-dose, this dose will not be accounted for compliance. In the case of a patient vomiting after 30min of MF intake, the dose will be accounted for compliance.

Patients in arm 2 used to continue MF intake after discharge at day 14 on an outpatient basis. Compliance during the 14 days treatment outside the hospital was assessed by collecting the empty blisters at the day 28 visit and checking for any unused drug. A diary including illustrations that is made understandable for illiterate subjects was provided to these patients in order to guide them in their treatment schedule at home. Any episode of vomiting reported by the patient was captured by the clinician at day 28 visit. In case of multiple episodes of vomiting, patients were instructed to come to the hospital for an assessment in an unscheduled visit. Compliance will be further assessed through cross-check with PK data.

Paromomycin administration

PM will be given for 14 days in both arm 1 and arm 2. Exact daily dose of 20 mg/kg will be calculated using patient's body weight and will be administered once-a-day with intramuscular injection into the buttock muscle.

PM sulfate will be supplied through IDA Foundation, Holland, in boxes of 10 amber-colored glass ampoules each, containing an equivalent 750 mg of PM base in 2 ml (375 mg/ml).

All administrations will be directly observed by the study nurse or clinician to assure compliance.

Treatment interruption

MF treatment in arm 1 (14 days) will last at least 13 days in order to be considered 90% compliant. In case of treatment interruption longer than 24 hours, missing doses will be compensated after day 14.

MF treatment in arm 2 (28 days) could be temporarily interrupted (due to AEs or at discretion of investigator) and resumed if this interval was no longer than 72hs. In this case, the total administered dose over a total of 25 days was still considered within 90% range of full compliance, therefore it was not considered a compliance deviation. The missing doses was not compensated after the final dose on day 28, and the

Confidential Page 36 of 68

schedule of assessments would remain the same.

If treatment needs to be interrupted for > 72hs due to an AE related to MF, or if treatment needs to be interrupted due to an AE related to PM or SSG, rescue treatment will be considered, at the discretion of the investigator.

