3.1. Study design

This is an open label, Phase III, randomized, controlled, parallel arm multicentre non-inferiority clinical trial to compare the efficacy of a combination regimen of MF and PM with SSG-PM for the treatment of primary adult and children VL patients in Eastern Africa.

In addition, safety of two combination regimens of PM (14 days) and MF (14 or 28 days) will be assessed, and the efficacy of the PM (14 days) and MF (28 days) investigational arm 2 will be described.

The study will be conducted at 5 LEAP sites and 2 MSF sites: Kacheliba in Kenya,

Confidential Page 23 of 68

Amudat in Uganda, Doka, Um El Kher and Tabarakallah (MSF) in Sudan and Gondar and Abdurafi (MSF) in Ethiopia.

The 2 treatment regimens to be tested were as below but with patient's recruitment in arm 2 now discontinued:

- Arm 1: Paromomycin 20 mg/kg/d IM for 14 days combined with oral miltefosine allometric dosing for 14 days
- Arm 2: Paromomycin 20 mg/kg/d IM for 14 days combined with oral miltefosine allometric dosing for 28 days (recruitment is now discontinued in this arm but patients' data available will be analyzed and results described)

The reference arm is the current standard treatment for VL:

Arm 3: Sodium Stibogluconate 20 mg/kg/day IM/IV combined with Paromomycin 15 mg/kg/day IM for 17 days

For patients weighing < 30 kg, an easy-to-use table with allometric dosing scheme by weight, height and sex will be provided to the investigators to define the exact daily dose to be administered. For patients weighing \geq 30 kg, the allometric dose will correspond to the conventional dose in mg/kg. Therefore, in order to simplify the dose calculation, patients weighing \geq 30 to < 45 kg will receive 100 mg/day and patients \geq 45 kg will receive 150 mg/day.

The target population will be VL patients from 4 to 50 years old in order to cover both paediatric and adult population. The limit of 50 years for inclusion is due to higher mortality rate and lower efficacy observed in patients > 50y when treated with SSG-PM in a recent pharmacovigilance program (Kimutai et al., 2017). MF and PM will be administered together, both starting at D1. PM dosage will be 20 mg/kg/d for 14 days administered once-a-day intramuscularly, whereas MF allometric dose will be administered orally BID for 14 days in arm 1 and for 28 days in arm 2.

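### At 30 kg the miltefosine dose in the text conflicts with the 30 kg row of the dosing tables for all girls and for boys under 120 cm, and no rounding rule says who that row is for

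*Combined protocol and SAP*

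**What the plan says.** Section 7.2.1 gives the dosing rule in weight bands. Below the threshold: "Patients <30 kg: the allometric MF daily dose will be calculated according to subject's weight, height and sex". From the threshold: "Patients ≥ 30 to <45 kg: 100 mg/day". The Protocol Summary and Section 3.1 give the same split at 30 kg. They also say that investigators receive a table by weight, height and sex from which to set the dose of patients under 30 kg.

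Under Miltefosine administration, Section 7.2.1 adds that for patients below 30 kg "the allometric dose will be defined according to weight, height and sex as indicated in Table 1". Two tables follow: "Table 1 - Daily allometric miltefosine dose for female children based on fat-free mass" and "Table 2 - Daily allometric miltefosine dose for male children based on fat-free mass". Both are laid out in whole kilograms and both end with a row labelled 30 kg. No note says whether weights are rounded, or for whom the 30 kg row is meant.

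Sections 7.2.1 and 10.5 define full compliance as 90-110% of the prescribed dose.

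**The concern.** A child recorded at 30 kg is covered by a fixed dose in the text and also by a height- and sex-dependent dose in the table that sites are given. Where these differ, the prescription depends on which part of the protocol a site follows. A child weighing, say, 29.6 kg raises the same question if the weight is rounded up before the rule is applied.

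The stakes are avoidable between-site variation in the tested regimen at a weight that the protocol itself treats as important. Section 1 reports lower miltefosine concentrations below 30 kg under conventional dosing, which is the reason for the allometric scheme. The prescribed dose is also the denominator of the compliance measure, and Section 10.8 plans to link individual exposure to cure and relapse.

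**Working it through.** **Inputs.** Text dose for 30 to under 45 kg: 100 mg/day, any height, either sex (Protocol Summary, Sections 3.1 and 7.2.1). Table doses: the 30 kg rows of Tables 1 and 2, both of which are legible.

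**Step 1: compare the 30 kg rows with the text.** Ratio = table dose / 100 mg.

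| Height (cm) | Table 1, girls (mg/day) | Ratio | Table 2, boys (mg/day) | Ratio |
|---|---|---|---|---|
| 80-89 | 50 | 50% | 60 | 60% |
| 90-99 | 60 | 60% | 70 | 70% |
| 100-109 | 60 | 60% | 80 | 80% |
| 110-119 | 70 | 70% | 80 | 80% |
| 120-129 | 70 | 70% | 100 | 100% |
| 130-139 | 80 | 80% | 100 | 100% |
| 140-149 | 80 | 80% | 100 | 100% |
| 150-159 | 80 | 80% | 100 | 100% |
| 160 | 80 | 80% | no entry | - |

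Mismatches: 9 of 9 female cells and 4 of 8 male cells, so 13 of 17. The text dose of 100 mg never appears in the female row.

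**Step 2: which mismatches matter in practice.** A boy of 100-119 cm weighing 30 kg has a BMI between 30/1.19² = 21.2 and 30/1.00² = 30. The documents describe a disease with weight loss and a population with much malnutrition, so such boys are probably rare. That is an inference, since the documents give no weight-by-height distribution. What remains is mainly girls, at 70-80 mg in the table against 100 mg in the text over 120-159 cm.

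**Step 3: what rounding would change.** For girls, the 29 and 30 kg rows of Table 1 agree at every height legible in both (50, 60, 60, 70 and 70 mg up to 129 cm; 80 and 80 mg at 140-159 cm). For them, rounding between table rows changes little. What changes the dose is whether a weight rounded to 30 kg then triggers the text rule. For boys, the two rows of Table 2 differ at 100-109 cm (70 against 80 mg) and 120-129 cm (80 against 100 mg).

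**Step 4: compliance.** Compliance = administered dose / prescribed dose. A girl prescribed 80 mg and given 80 mg has 80/80 = 100%. A girl prescribed 100 mg and given 100 mg has 100/100 = 100%. Only if the denominator is later taken from the other source do the figures become 80/100 = 80% or 100/80 = 125%, both outside 90-110%.

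**Step 5: the table citation.** The sentence for patients under 30 kg names Table 1 only. The two tables are not interchangeable: of 88 cells from 13 to 29 kg that can be read in both, 82 differ, and the male dose is then 10-30 mg higher. Cells left blank or broken by the PDF reading were skipped.

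**The case against.** The strongest reply is that the text is consistent wherever it appears: tables below 30 kg, fixed dose from 30 kg. A site following it never enters a table for a child of 30 kg or more. The 30 kg row is then a surplus boundary row, perhaps meant for weights just under 30 kg that round up. A step at 30 kg exists under the text rule in any case: girls of 140-159 cm have 80 mg at 29 kg and 100 mg at 30 kg.

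Much of this stands, and it narrows the point to one row. It does not remove the point, because the rounding explanation is stated nowhere and the table is the tool sites are given for setting the dose.

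Three stronger readings are tempting, and the documents do not support them:

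- **Boys are sent to the female table.** The sentence that cites Table 1 also makes sex a determinant of the dose. A table labelled for male children follows directly and appears in the list of tables. This is an incomplete cross-reference.
- **The gap itself misclassifies compliance.** Compliance is measured against the prescribed dose, so the gap alone moves nobody out of the band (Step 4). The documents describe no recalculation from another source.
- **The row will cause relapses.** Section 1 discusses exposure and relapse in general, and compares children with adults and dosing regimens with each other. It offers nothing about a one-kilogram boundary, and no exposure calculation supports that step.

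**Conclusion.** The conflict is real and confined to children recorded at or rounded to 30 kg. The table gives 50-80% of the text dose for girls (70-80% at 120-159 cm) and 60-80% for boys under 120 cm. There is no conflict for boys of 120 cm or more.

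The number of children affected is not given and is probably small. The sample size, margin and primary test are untouched. The risk is inconsistent prescribing between sites in the miltefosine arms, and an ambiguous prescribed dose for compliance and exposure work if it was not recorded with its source. Missing Table 2 in the citation is a minor editorial matter.

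The conclusion rests on the 30 kg rows as they appear in the document and on the absence of any rounding rule there. Training material or site instructions may contain one, but the protocol does not. No view is taken on which dose is right.

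**What to change.** - Reconcile the 30 kg row of Tables 1 and 2 with the weight-band text in the Protocol Summary and Sections 3.1 and 7.2.1, so that one instruction applies at 30 kg. The choice is the sponsor's.
- State how weights between 29 and 30 kg are read into the tables, and whether the 30 kg threshold applies to the measured or the rounded weight.
- Identify patients already dosed at a recorded weight of 30 kg, including those rounded to it. For each, list the prescribed dose that was used, and keep that dose as the reference in the compliance and exposure analyses.
- As a minor correction, cite Table 1 for female and Table 2 for male patients in the sentence that now reads "height and sex as indicated in Table 1".

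The cost is a protocol clarification, a site memo and a short listing from existing dosing records. The sample size does not change.

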These modifications in agreement with the DSMB will ensure retention of the investigational arm 1, on the basis of 1) shorter treatment duration than current standard of care, 2) it can be administered within the hospitalization period, 3) it is a cheaper option for the control programs, and therefore from a public health perspective will be a potentially more favorable option for patients.

In this revised protocol version, the analysis remains as planned, but comparison will be performed only between one investigational arm (arm 1 MF/PM 14 days) and the standard of care (SSG-PM). Data from patients randomized in arm 2 (PM 14 days/MF 28 days), which recruitment is now stopped, will be summarized in a descriptive analysis, but not included in the formal comparative efficacy analysis.

The current study aims to determine the safety and efficacy of one combination regimen of PM and MF as compared to SSG-PM for the treatment of primary VL patients in Eastern Africa. This is an open label, Phase III, randomized controlled, parallel arm multicentre non-inferiority clinical trial. The investigational arms are:

- Arm 1: Paromomycin 20 mg/kg/d IM for 14 days combined with oral miltefosine allometric dosing BID for 14 days
- Arm 2: Paromomycin 20 mg/kg/d IM for 14 days combined with oral miltefosine allometric dosing BID for 28 days (recruitment is now discontinued in this arm)

The control arm is the current standard treatment for VL in East Africa:

 Arm 3: Sodium Stibogluconate 20 mg/kg/day IM/IV combined with Paromomycin 15 mg/kg/day IM for 17 days

MF allometric dosing will be calculated according to patient's weight, height and sex. For patients weighing < 30 kg, an easy-to-use table with allometric dosing scheme by weight, height and sex will be provided to the investigators to define the exact daily dose to be administered. For patients weighing \geq 30 kg, the allometric dose will correspond to the conventional dose in mg/kg. Therefore, patients weighing \geq 30 to < 45 kg will receive

Confidential Page 15 of 68

100 mg/day and patients ≥ 45 kg will receive 150 mg/day.

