To overcome this under-dosage of children, an allometric dosage for paediatric VL has been assessed in the LEAP 0714 trial in Kenva and Uganda. This MF dosing is based on an allometric algorithm by fat free mass. In practice, individual weight, height and sex are used to determine the dose, which entails administering a relatively higher mg/kg/day dose in patients with lower body weight compared to patients with a higher body weight (Dorlo et al., 2012). The 28 days regimen of MF allometric dose showed a cure rate of 96.7% (95% CI: 82.8-99.9%) at Day 28 and a cure rate of 90.0% (95% CI: 73.5-97.9%) at 6 months follow up in a population of 30 patients aged 4 to 12 years. These results showed that efficacy level was increased in children treated with the allometric dose as compared to the conventional dose, reaching similar efficacy observed in adults in the LEAP0208 trial (i.e. 86.2%). In general, MF was well tolerated and compliance in the hospital setting was 100%. There was no treatment discontinuation due to drug related adverse events. Two SAEs were reported (anaemia and transfusion reaction), none of them related to MF, which is consistent with the good safety profile of this drug. PK analysis was performed to further characterize the drug exposure and PK properties of MF comparing allometric versus historic data on the conventional regimen. The overall MF exposure (area under the concentration-time curve from zero to infinity) was 12% higher compared to conventional dosing in the same pediatric age group. MF seemed to accumulate faster in LEAP0714 with the allometric dosing in the first week of treatment, resulting in a higher drug exposure during the first half of the treatment: e.g. day 7 MF concentrations were generally much higher for LEAP0714 (median 5,880 ng/mL) than for LEAP0208 (median 2,670 ng/mL), although this difference was not significant due to high variability. While total MF exposure was thus increased, children treated with MF allometric dosing did not achieve the expected exposure i.e. similar to adults treated with conventional therapy of 2.5 mg/kg/d for 28 days. A potential reason for this was an apparent stagnation of the MF accumulation between day 14 and day 21 for 40% of the LEAP0714 patients. after which MF concentrations rose again between day 21 and day 28. Nevertheless, the variability in MF concentrations and overall exposure was higher for the linear dosing regimen than for the allometric regimen. This had an effect on the proportion of patients reaching a PK target threshold, with less patients being low exposed. It was previously shown that the duration someone was above 10x EC50 (17.9 µg/mL) as measure of MF PK was associated with a lower probability of disease relapse and subsequent rescue treatment (T. P. C. Dorlo et al., 2014). 15% of paediatric patients enrolled in LEAP0714 did not reach the 17.9 µg/mL threshold (10xEC50), compared to 29% for LEAP0208 in the paediatric subset. This in combination with the 12% overall higher total exposure to miltefosine could possibly explain the improved clinical efficacy observed in children treated with the allometric regimen.

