In order to mitigate the low enrollment, the protocol was amended to v3.0 dated 4 May 2018 to include 2 MSF sites (Tabarakallah in Sudan and Abdurafi in Ethiopia). The sites were expected to compensate for the low patient numbers overall. In addition, because of the high proportion of patients in Ethiopia excluded due to severe malnutrition (30-40%), an Ethiopia-specific amendment was implemented to modify the indicator for severe malnutrition from body mass index (BMI) to mid-upper arm circumference (MUAC) to allow for a better representativeness of the Ethiopian population. Finally, active case search and referral networks were initiated at some of the sites. Nevertheless, these measures taken to improve recruitment have not resulted in a significant boost of the enrolment and further actions needed to be taken.

New oral promising NCEs are expected to be at the clinical stage of development for VL patients by 2021 and the plan is to complete this trial before then so that results can be of benefit to the VL patients. Moreover, if new trial(s) with NCEs start before the end of this study, the recruitment of patients will compete with these NCEs studies and will become even more challenging to develop new treatments for visceral leishmaniasis in Eastern Africa region.

Following DSMB review of the available data (meeting held on 7 May 2019), two main changes to the protocol were agreed to achieve completion of the trial in an acceptable timeframe and ensure the achievement of the objectives of the trial. First, to revise the exclusion criteria in order to include a more VL representative population, and second, to discontinue recruitment in the investigational arm 2.

Revision of the exclusion criteria. The reasons for exclusions leading to a low enrollment rate were analyzed. It was noted that across the sites, 15 to 20% of patients were excluded because of laboratory abnormalities. In most cases, the baseline laboratory abnormality was not considered clinically significant by the investigator to indicate AmBisome therapy and a majority of these patients were therefore treated with SSG-PM with a good therapeutic response. For this reason, individual laboratory parameters in the exclusion criteria were replaced by investigator judgement on the need of AmBisome, based on the severity of the clinical manifestations of the disease (such as jaundice, bleeding and oedema) and laboratory parameters.

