4.2. Exclusion criteria

The presence of any of the following will exclude a subject from study enrolment:

Patients who are relapse cases

Confidential Page 27 of 68

- Patients with Para-Kala azar dermal leishmaniasis grade 3
- Patients who have received any anti-leishmanial drugs in the last 6 months
- Patients with severe malnutrition (for children aged <5 years: weight-for-height WHO reference curves by sex, z score <-3; for patients 5-18 years: BMI-for-age WHO reference curves by sex, z score < -3; for adults >18 years: BMI < 16)*
- Patients with positive HIV diagnosis
- Patients with previous history of hypersensitivity reaction or known drug class allergy to any of the study treatments
- Patients with previous history of cardiac arrhythmia or with a clinically significant abnormal ECG
- Patients suffering from a concomitant severe infection such as TB, schistosomiasis or any other serious underlying disease (e.g. cardiac, renal, hepatic) or chronic condition which would preclude evaluation of the patient's response to study medication
- Pregnant or lactating women
- Female patients of child bearing age who do not accept to have a pregnancy test done
 at screening and/or who do not agree to use contraception from treatment period until
 5 months after the end of treatment (see section 15.2)
- Patients with haemoglobin < 5g/dl
- Patient with signs of severe VL according to Investigator's judgement, requiring an indication for AmBisome therapy based on the clinical manifestations (such as jaundice, bleeding, edema) and clinically significant abnormalities in the following laboratory parameters: haemoglobin, WBC, platelets, liver enzymes (ALT and AST), total bilirubin and creatinine
- Patients with pre-existing hearing loss based on audiometry at baseline
- Patients who cannot comply with the planned scheduled visits and procedures of the study protocol

Confidential Page 28 of 68

^{*} Note: for Ethiopia only: Patients with severe malnutrition (for patients 4-18 years: MUAC cut-off based on MUAC-for-height reference table; for patients > 18 years: MUAC < 170 mm)

5. Schedule of events

Protocol Activities and Forms to Be	Screening		Treat		Follow up visits			
Completed	D-7 to D0	D1	D3	D7	D14	D28 (EOT) +1d	D56 +/- 7d	D210 +/- 14d
Consent form & consent for HIV test	X							
Demographic data and medical history	Χ							
Clinical assessment	X	X	X	Х	X	X	X	X
Nutritional status	Χ							
Audiometric test	Χ				X	X		X
HIV test	Χ							X ¹

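### An Ethiopian child who passes the MUAC criterion could be randomised to arm 1 without a protocol-defined miltefosine dose, because the undosed area of Tables 1 and 2 still relies on the WHO curves

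*Combined protocol and SAP*

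**What the plan says.** **Dose source.** For arm 1, section 7.2.1 states: "For patients less than 30 kg, the allometric dose will be defined according to weight", height and sex, and cites Table 1. Table 1 covers girls and Table 2 covers boys. The protocol summary and section 3.1 give the table's purpose: an "easy-to-use table with allometric dosing scheme by weight, height and sex will be provided to the investigators to define the exact daily dose". Section 7.2.1 also says that "the allometric MF daily dose will be calculated according to subject's weight, height and sex", but prints no formula. Section 1 names the method ("This MF dosing is based on an allometric algorithm by fat free mass") and cites a publication without reproducing the equation.

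**Undosed area.** In both tables the cells for low weight at a given height are empty. They carry only the severe-malnutrition notice and the pointer to the WHO curves.

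**Eligibility outside Ethiopia (4.2).** Children are excluded on WHO z-scores: weight-for-height under 5 years and, above that, "for patients 5-18 years: BMI-for-age WHO reference curves by sex, z score < -3".

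**Eligibility in Ethiopia (4.2, 8.2).** A note substitutes a different test: "for Ethiopia only: Patients with severe malnutrition (for patients 4-18 years: MUAC cut-off based on MUAC-for-height reference table". The table in 8.2 sets the MUAC cut-off by height alone. Section 1 explains that the amendment was made to "modify the indicator for severe malnutrition from body mass index (BMI) to mid-upper arm circumference (MUAC"), because severe malnutrition had excluded 30-40% of patients in Ethiopia. It is a replacement, not an added criterion.

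Ethiopia-specific notes appear in 4.2, 8.2, 8.3.1 and 10.4. Section 7.2.1 has none.

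**The concern.** The tables leave cells empty on the premise that a WHO-based criterion deals with children who are too thin. In Ethiopia that criterion was withdrawn and the tables were not adapted. A site that follows the text could find a child eligible, request a randomisation code under section 6 (which does not call for a table lookup first), and then discover that arm 1 has no miltefosine dose for that child.

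Two outcomes are then possible. The child may receive a dose that the protocol did not plan. Exposure in a very thin patient is then undefined, and the compliance rule (90-110% of what was prescribed) has no protocol reference. Or the child may be lost after allocation in arm 1 only, because SSG and paromomycin in arm 3 are dosed in mg/kg (7.2.2). Section 9.3 does not replace withdrawn subjects.

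**Working it through.** The plan states no figure to reproduce. The check sets the dosing tables against the eligibility criteria.

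**Inputs.** Dosed and empty cells of Tables 1 and 2, as readable (7.2.1); MUAC cut-offs by height (8.2); BMI = weight in kg / (height in m)².

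**Step 1. Edge of the undosed area.** Isolated gaps inside the dosed region were treated as losses in text extraction.

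| Height (cm) | First dosed weight, girls | First dosed weight, boys | Ethiopian MUAC exclusion (8.2) |
|---|---|---|---|
| 110-119 | 14 kg | 15 kg | < 120 mm |
| 120-129 | 17 kg | 18 kg | < 125 mm |
| 130-139 | 21 kg | 21 kg | < 135 mm |
| 140-149 | 23 kg | 24 kg | < 145 mm |
| 150-159 | 26 kg | 28 kg | < 150 mm |

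**Step 2. BMI at the edge.** For the heaviest undosed row in each column, BMI was computed at both ends of the height band.
- Boys, 110-119 cm, 14 kg: 14/1.19² = 9.9 to 14/1.10² = 11.6.
- Girls, 120-129 cm, 16 kg: 16/1.29² = 9.6 to 16/1.20² = 11.1.
- Boys, 150-159 cm, 27 kg: 27/1.59² = 10.7 to 27/1.50² = 12.0.

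Over all columns the range is 8.4 to 12.0. The lowest value (girls, 100-109 cm) comes from rows that are scrambled in the text. From 110 cm upward the range is 9.2 to 12.0.

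**Step 3. A case.** Take a boy of 112 cm and 14 kg with MUAC 122 mm. His BMI is 14/1.12² = 11.2. He passes the Ethiopian criterion, since 122 mm is not below 120 mm. His column starts at 15 kg, so no dose is shown. The case is constructed; it shows what the text permits, not that such a child was seen.

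**Step 4. Are the empty cells simply thinner than every dosed cell?** No, because heights are grouped in 10 cm bands. A boy of 110 cm and 14 kg (BMI 11.6) has no dose, while one of 119 cm and 15 kg (15/1.19² = 10.6) has one. A boy of 150 cm and 27 kg (BMI 12.0) has none, while one of 159 cm and 28 kg (28/1.59² = 11.1) has one.

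**Step 5. Scale for the primary comparison.** One patient in an arm of 170 is 1/170 = 0.6 percentage points, against a non-inferiority margin of 7 points.

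**The case against.** The strongest reply is that the affected group is hypothetical. The documents hold no joint data on MUAC, weight and height, and a child with BMI near 9-12 may usually fail the MUAC cut-off too. That stands: the count could be zero. A reader might take the 30-40% as its size, but that figure is the share of Ethiopian patients excluded for severe malnutrition, with no age limit stated. It is not the share under 30 kg or in undosed cells.

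The table edge is also uncertain. Some dosed cells were lost in extraction, and the boy in step 3 is one row below the first readable dose. This weakens the single example. It does not remove the labelled undosed area, which appears in both tables.

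Sites are not without recourse. Weight and height are measured at screening. Section 4 asks for all relevant conditions to be weighed and sends eligibility questions to the sponsor's medical coordinator before enrolment. Section 4.2 still excludes severe VL and serious underlying disease. So it would be too strong to say that a child is eligible whatever the weight for height, or that a site must improvise a dose. But nothing obliges a site to notice the empty cell before randomisation, and the coordinator route does not put a dose in the protocol.

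A reader might also infer that such a child necessarily drops out of the primary analysis set. Section 10.2 does not support that. One dose of study treatment is enough for mITT, and arm 1 includes paromomycin in mg/kg from day 1. Only a child given no study drug at all would leave.

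**Conclusion.** The inconsistency is in the text and holds in a limited form. Below 30 kg, Tables 1 and 2 are the only operational source of the miltefosine dose. Their undosed area depends on a criterion that Ethiopia replaced, and the MUAC criterion does not keep an otherwise eligible child out of it. Such a child could enter arm 1 without a protocol-defined dose.

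The reach is patients under 30 kg at two of seven sites, with very low BMI, in a number that is unknown and may be few or none. At 0.6 points per patient, no material bias in the non-inferiority comparison is shown. The reasons to act are exposure in individual thin children and the avoidance of losses in one arm only.

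This rests on reading the labelled empty area as intended, and on MUAC being a replacement, as section 1 says. The WHO values are not in the documents, so whether the empty cells match the z-score exclusion at the other five sites could not be checked.

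**What to change.** The sponsor should reconcile the Ethiopian MUAC note in 4.2 and 8.2 with the undosed area of Tables 1 and 2, so that the protocol states what applies to a MUAC-eligible child in an undosed cell. Section 6 or the screening checklist should require the table cell to be looked up at screening. Any undosed cell should be referred to the sponsor before the randomisation code is requested, so that the question is settled without knowledge of the arm. In the same edit, the sentence in 7.2.1 that cites only Table 1 should also cite Table 2.

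The cost is one protocol clarification and one checklist line. How the sections are reconciled is for the sponsor; no dose and no eligibility rule is proposed.
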